Study Protocol and Statistical Analysis Plan

Title: A Personalized Behavioral Intervention for Older Adults with Musculoskeletal Pain and Sleep Complaints

NCT03921840

Date: 9/1/2020

1. Abstract

It is well recognized that physical activity/exercise is an effective intervention to improve sleep, reduce pain and improve function in a variety of pain conditions. Traditional interventions to increase physical activity are challenging in older adults due to extensive staffing requirements and low adherence. We plan to conduct a pilot trial in a cohort of older adults (without dementia) with both chronic musculoskeletal pain and nocturnal sleep complaints to test the effectiveness of a 12-week personalized behavioral intervention (compared to a control group) embedded within a smartwatch application in older adults. 20 cognitively intact elders will be enrolled and randomly allocated to intervention or control group. Participants in the intervention arm will receive a 2-hour in person education session, and personalized, circadian-based activity guidelines, with real time physical activity self-monitoring, interactive prompts, biweekly phone consultation with the research team, and financial incentives for achieving weekly physical activity goal. The control group will receive general education on physical activity in older adults and continue their routine daily activity for 12 weeks.

2. Objectives

This study aims to examine 1) the feasibility and acceptability of a personalized behavioral intervention implementing mobile health technology for promoting pain, sleep, and mood in older adults with chronic pain and sleep complaints. 2) The preliminary efficacy of the study on pain and sleep outcomes

3. Background

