Screening (30minutes): After informed consent, the research team will assess (maximum of 30 minutes) the participants' eligibility for intact Cognition using the Montreal Cognitive Assessment (MOCA) and poor sleep quality by asking "do you have problems with your sleep? Do you feel refreshed after sleep?", and pain by asking "Are you currently troubled by physical pain, either all the time or on and off? Has this pain persisted for at least 3 months?", and readiness for performing regular exercise using the physical activity readiness questionnaire (PAR-Q). Participants who passed the PAR-Q are eligible for participation. For those who failed to pass the PAR-Q, medical clearance along with information about specific exercise limitations needs to be obtained from their primary care providers in order to participate. People who fail to pass the screening will drop the study after the screening process.

Randomization: Eligible participants will be randomly allocated to either intervention or control group (1:1) using blocked randomization with a block size of 4. A computer-based assignment scheme will be used to determine the participant's group assignment.

Intervention description: Based on the self-efficacy theory, participants in the intervention arm will receive personalized, circadian-based activity guidelines, 2 or 3 1-hour in person education session, real time physical activity self-monitoring, interactive prompts, biweekly phone consultation with the research team, and financial incentives for achieving weekly physical activity goal.

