Data management: We will use the REDCap data entry and management system. Data from screening, baseline, intervention sessions, and post-intervention data collection will be entered into forms that the data manager will check for completeness and appropriateness. The data manager will send reports of missing or inappropriate entries to the PI every week for clarification and resolution. **Data that cannot be stored on the REDCap will be stored at either a locked cabinet at the research coordinator (MoCA cognitive screening) / assistants' offices at the JHU School of Nursing or at a folder as electronic files on the JHU box (actigraph data and cognitive assessment, and fitabase data) that could only be accessed by the study team.**

Measurement

Sleep Measures: We will use the Actiwatch to objectively assess nocturnal sleep in terms of total nocturnal sleep time, sleep latency, and wake after sleep onset (WASO); the smartwatch cannot be used to measure sleep due to its need for overnight charging. The Pittsburgh Sleep Quality Index, Epiworth Sleepiness Scale and Insomnia severity index will be used for subject screening and assessing sleep quality subjectively. A two-week sleep diary will be used to confirm Actiwatch-based nocturnal sleep. It will provide information on nap frequency and duration, as well as nocturnal sleep duration. Total nocturnal sleep time is the primary sleep measure, and all others are considered secondary.

Pain Measures: Presence of pain will be determined by affirmative answers to both of the following questions: (1) "Are you currently troubled by physical pain, either all the time or on and off?" and (2) "Has this pain persisted for at least 3 months?" [13]. Older adults answering yes to both questions will then be asked to specify the duration of pain and the pain sites. Pain intensity, severity, and interference with daily life will be measured by two instruments: (1) The brief pain inventory (locations and severity of pain) and (2) PROMIS pain measures (pain intensity, interference, and behaviors). Pain Self-Efficacy will be measured by the Chronic Pain Self-Efficacy Scale.

Fatigue will be assessed by the FACIT Fatigue Scale.

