7.1. Sample characteristics: We will compare the values of demographic and baseline clinical variables between the two study arms using t-tests or Mann-Whitney U-tests for continuous variables and chi-squared or Fisher’s exact tests for categorical measures. This analysis will both describe the overall study sample and confirm that randomization resulted in the expected balance between covariates of interest;

7.2 Descriptive analysis will be used to describe the feasibility data;

7.3 Preliminary efficacy: Repeated Measures ANOVA will be performed to examine if the proposed intervention increases the participants’ proposed outcomes compared to the control arm. Analyses will examine the interaction (Time × Group) to access whether there are differences in changes in outcome variables between the two arms. The initial effect size of the intervention will be determined based on results of pain outcomes.

8. Risks

Minimal risks to study participants are expected. There is minimal risk associated with physical activity. We will explain associated risk to the participants. In very rare occasions, the subject may fall or get

injured during physical activities. These adverse events should be minimized by using personalized physical activity plans, which will be developed/designed by the exercise trainer to be most suitable for the subject based on the subject's personal features. Some environmental factors (e.g. weather) may impact on the participant's safety when they perform physical activity outside. We will advise participants of this safety information during the exercise intervention. For example, we will advise them to perform indoor physical activities in the following weather conditions: temperature lower than 32°F or higher than 90°F, rainy, snowy or heavy windy weather. We will also advise them to hydrate during performing physical activity and hot weather. The activity intervention will be based on an existing NIH-funded activity protocol for older adults. Finally, the study participant's primary care provider will be contacted to confirm that the study participant can safely engage in the activity regimen.

Subjects may experience psychological reactions to completing the questionnaire data and cognitive tests. Since the questions are benign, the risk is minimal.

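### Section 7.3 does not say which of at least four pain scores gives the initial effect size, and it does not ask for an interval; a pre-named, baseline-adjusted estimate would settle both at almost no cost

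*Combined protocol and SAP*

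**What the plan says.** Objective 2 of the protocol is "The preliminary efficacy of the study on pain and sleep outcomes". SAP section 7.3 addresses it with a repeated measures ANOVA and its Time × Group interaction, and ends: "The initial effect size of the intervention will be determined based on results of pain outcomes". That sentence names no score, formula, standardiser or interval.

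Under Measurement in section 4, the Pain Measures paragraph states that "Pain intensity, severity, and interference with daily life will be measured by two instruments". The first is "The brief pain inventory (locations and severity of pain"), and the second is "PROMIS pain measures (pain intensity, interference, and behaviors"). This makes at least four scores: Brief Pain Inventory severity and three PROMIS scores. Pain self-efficacy, listed in the same paragraph, is a fifth if it is counted as a pain outcome.

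The only ranking of outcomes is in the Sleep Measures paragraph: "Total nocturnal sleep time is the primary sleep measure, and all others are considered secondary". From its position and wording it ranks the sleep measures and does not order the pain scores.

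**The concern.** The sentence in 7.3 speaks of one effect size but several outcomes. Two analysts who followed it faithfully could report different numbers, and a reader could not tell whether the score had been settled before or after the results were seen. The domain with a named primary measure (sleep) is absent from the sentence, while the domain without one (pain) supplies the figure.

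Two things are at stake. First, if the score were chosen for its result, the reported effect would be biased upwards. Second, at this sample size any single value is so imprecise that it says little without its interval. If someone later used the bare value to size a trial, that trial could be too small.

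**Working it through.** **Inputs from the documents.** Total sample 20 (Abstract); 1:1 allocation in blocks of 4 (Randomization), so 20/2 = 10 per arm in 20/4 = 5 full blocks; two time points, before and after the intervention (Data collection). The documents give no alpha, power, SD or target effect, so there is no stated sample-size calculation to reproduce.

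**Assumptions.** A common correlation *r* of 0.3 to 0.7 between pain scores; the same true standardised effect of 0.3 on each; two-sided alpha 0.05 and 80% power for a later trial; a pre-post correlation ρ of 0.3 to 0.7; no dropout unless stated.

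**Step 1. Precision without any selection.** With two time points, the Time × Group test is the two-sample t-test on change, with 18 degrees of freedom. Inverting the noncentral t distribution with t = d × √(10/2) gives:

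| Observed d | 95% CI | Width |
|---|---|---|
| 0.3 | -0.59 to 1.18 | 1.77 |
| 0.5 | -0.40 to 1.38 | 1.78 |
| 0.8 | -0.12 to 1.70 | 1.82 |

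The width is about 1.8 SD throughout. With 8 completers per arm (an assumption), d = 0.5 gives -0.51 to 1.49.

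**Step 2. What selection could add.** The standard error of d is about √(2/10) = 0.447. For *k* equally correlated estimates with the same mean, the expected largest is 0.3 + 0.447 × √(1 − r) × E(k), where E(k) is the expected maximum of *k* independent standard normals: 1.029 for k = 4 and 1.163 for k = 5.

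| Scores | r = 0.3 | r = 0.5 | r = 0.7 |
|---|---|---|---|
| 4 | 0.69 | 0.63 | 0.55 |
| 5 | 0.74 | 0.67 | 0.58 |

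For example, k = 4 and r = 0.7 gives 0.3 + 0.447 × 0.548 × 1.029 = 0.55. Simulated trials that also carry the small-sample bias of d run slightly higher: 0.59 for that case, and 0.78 for k = 5 with r = 0.3. In the same simulations a single pre-named score averages 0.31, close to the true 0.3.

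**Step 3. What that could mean later.** The number per arm is 2 × (1.96 + 0.84)² / d² = 15.70 / d². A true 0.3 needs 15.70/0.09 = 174.4, so 175 per arm. Planning on 0.55 gives 15.70/0.3025 = 51.9, so 52. Planning on 0.74 gives 15.70/0.5476 = 28.7, so 29. If the truth were 0.3, trials of 52 and 29 per arm would have about 33% and 20% power.

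**Step 4. Change score against baseline adjustment.** With equal variance σ² at both times, the between-arm difference in change has variance proportional to 2σ²(1 − ρ). ANCOVA on the post-intervention score has σ²(1 − ρ²), multiplied by (N − 3)/(N − 4) = 17/16 for estimating the slope with N = 20. The ratio of ANCOVA to change is (1 + ρ)/2 × 17/16:

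- ρ = 0.3: 0.65 × 1.0625 = 0.69
- ρ = 0.5: 0.75 × 1.0625 = 0.80
- ρ = 0.7: 0.85 × 1.0625 = 0.90

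The adjusted estimate has 10% to 31% less variance, from data that the trial already collects. Residual degrees of freedom fall from 18 to 17.

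**The case against.** The strongest reply is that 7.3 is silent on these points and does not set a bad rule. Every observed effect size is based on results. The plural also fits reporting one effect size for each pain score, in which case nothing is selected and the bias in Step 2 does not arise. An interval is neither promised nor excluded. The trial is a 20-person pilot whose first objective is feasibility and acceptability, and its efficacy aim is labelled preliminary.

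Much of this stands, and it rules out several stronger readings that a reader might infer:

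- That the score will be picked after the data are seen, or that only a point value will be given. The text says neither; it leaves both open.
- That a later trial will be sized on this figure. The word initial in a pilot suggests it, but no later use is stated. Without selection, a noisy estimate can mislead in either direction.
- That sleep contributes nothing. Sleep is in objective 2 and falls under the Time × Group test; it is missing only from the effect-size sentence.
- That the effect size is the pilot's main result. The documents do not call it that.

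It can also be objected that adjusting for baseline departs from the planned ANOVA, so that estimate and test would come from different models. That is fair, and it is met by using the adjusted model for both. Baseline data are collected after randomisation in an unblinded trial, so self-reported baselines could be affected by knowledge of the arm; change scores rely on the same baseline, so this does not argue for keeping them.

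The reply does not supply a lead pain score or an interval. Pilot status makes the interval more useful, because at 10 per arm it is most of what the estimate can convey.

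**Conclusion.** The point holds as a gap in definition, together with an improvement that needs no new data. As written, 7.3 does not identify the number it will produce. The imprecision is the firmer part: an interval about 1.8 SD wide follows from 10 per arm and needs no assumption about selection or correlation. The inflation is conditional. An average of 0.55 to 0.74 for a true 0.3 requires that the largest of four or five scores is reported, that true effects are equal and that correlations lie between 0.3 and 0.7; the documents state none of these. Those figures are not a ceiling, since lower correlations would raise them, and they fall to no selection bias at all if every score is reported or one is fixed in advance. The gain from baseline adjustment (variance ratio 0.69 to 0.90) rests on assumed pre-post correlations of 0.3 to 0.7 and equal variances. None of this threatens the validity of the trial.

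**What to change.** Replace the last sentence of 7.3 with a definition along these lines:

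- The effect size is the between-arm difference in the post-intervention score, adjusted for baseline by ANCOVA, with its 95% confidence interval. It is given in the measure's own units and in standardised form, with the standardiser stated and Hedges' small-sample correction applied.
- It is reported for total nocturnal sleep time and for one pain score that the sponsor names now, before outcome data are examined.
- The same ANCOVA replaces the Time × Group test for efficacy, so that estimate and test agree.
- The other pain scores are reported alongside, in the same form, as secondary.
- The interval, and not the point value alone, informs any later trial.

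The cost is one residual degree of freedom (18 to 17) and a short SAP edit. No extra participants, visits or measurements are needed.

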Our proposed theory-derived intervention is guided by theoretical constructs from the self-efficacy theory. Self-efficacy, one's confidence in the ability to perform particular behaviors, influences the performance of those behaviors, which in turn impacts health outcomes. Enactive mastery experiences, verbal persuasion, vicarious experiences, and physiological/ emotional status are the four principle sources of self-efficacy beliefs. Evidence illustrates that physical activity interventions designed based on self-efficacy concepts

effectively promote physical activity in older adults. The personalized behavioral intervention, which includes physical activity training, exercise prescription, goal setting, phone coaching, consultation, and feedback, real-time physical activity self-monitoring, interactive prompts and feedback with smartwatch, and weekly financial incentives will provide older adults with a stronger sense of self-efficacy. This will engage them in physical activity.

4. Study Procedures

Overview of study design: This is a two-group randomized controlled trial to test the effectiveness of a 12-week personalized behavioral intervention implementing smartwatch technology in promoting physical activity, pain, and sleep in older adults in comparison with a control group. We aim to enroll 20 eligible participants in one years and complete the study in 18 months. Length of a subject's participation time in study will be 16-18 weeks in total, which includes 2-3 week of screening and pre-intervention data collection, 12-week intervention/control period, and 2-3 week post-intervention data collection. It is an unblinded trial. Due to the nature of the intervention (ongoing communication between research team and participants), it is impossible to blind the group assignment from the participants and the research team.

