The personalized circadian-based activity guideline will be developed based on the individual's typical daily circadian profile, functional status, and preference for exercise. We will advise participants to take afternoon naps (<90 minutes) and avoid napping after 4pm and before 8pm. The research team will work with a certified exercise trainer to develop the personalized physical activity plan for each subject. An afternoon nap of the optimal duration will be advised as healthy napping. All participants will be instructed to nap during this timeframe and to avoid any naps at other times of the day, especially in early evening. The individual's typical circadian profile will be calculated from the two-week baseline Actigraph data. The participant will receive a 30-minute instruction session from the research team session to provide instructions of how to follow the personalized activity guidance and use the study devices. A smartwatch (Fitbit Versa) and a paired smartphone (if the participant does not have a smart phone) will be distributed to participants.

In person training: Participants will receive a 2 or 3 1-hour in person education sessions with the exercise trainer which includes a 20-minute general education on exercise in older adults and a 40-minute education on personalized exercise and participating the study intervention. Session 1 will be within one week after the baseline; Session 2 will be scheduled 2-3 weeks after session 2. All participants in the intervention group will have session 1 and session 2. If the trainer feels the participant need another session to perform the exercise independently, session 3 will then be scheduled as needed. To facilitate the participant's exercise at home, we will provide a set of dumbbell and resistance band for them to use during the study. The education session will be designed using materials from the Go4Life program from the National Institute on Aging (<https://go4life.nia.nih.gov>). The participant will receive a copy of Go4Life program book and can find instructions for all selected exercise in the program book.

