Self-monitoring: Subjects will self-monitor their level of physical activity (steps & minutes of moderate activity) using the smartwatch. The Google calendar and Fitbit apps will send messages and alerts to the subject's smartwatch that encourage them to achieve their daily goals. For example, a participant may typically be inactive for a long period (e.g., >90 minutes) at 10AM. In this case, the research assistant will program the smartwatch to pro-actively chime or vibrate at 10AM each day with a reminder message through Google Calendar. Similarly, if the smartwatch detects a long sedentary period, the Fitbit app will automatically send an alert via the smartwatch to motivate the subject to increase their physical activity. The smartwatch will be removed every 3-4 days for charging. If a participant has low activity for 3 consecutive days, the research assistant will call the participant to either encourage them to adhere to the plan or provide a modified plan after consulting the exercise trainer.

Phone consultation: Subjects will have biweekly phone consultation with the research team members to receive guidance and adjustment on activity plans. Recognizing that changing behavior is a process, the personalized activity plan will be less intense at the beginning and adjusted every two weeks based on participant's data during the previous two weeks.

Description of control condition: The control group will receive general education on physical activity for older adults and continue their daily activity and healthcare routine. They will also receive a Go4Life program book from the National Institute on Aging.

Data collection includes pre-intervention (baseline, 2weeks) and post-intervention (2weeks). The data collection will take place in a private room at the School of Nursing, a clinic office or the participant's apartment per the participant's preference.

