The risk of breaching study participant confidentiality will be minimized by identifying all participants by code numbers and securing all data collected in locked files in the PI's office and screening information to locked file cabinets with limited staff access. Pre-coded data collection instruments are prepared for use with study participants at each testing occasion. Identification numbers to assure subject confidentiality will be used. Only one master log of subject name, address and telephone number and study identification assignment will be maintained in a password protected computer program. Access to these computer files will be password protected, recordings will not contain respondent name or other personal identifying information.

Financial risks to the participants: There are no anticipated financial risks to the participants.

Plan for Data and Safety Monitoring: Aligned with NIH/NINR guidelines, the proposed study is a single site, small scale clinical trial which involves minimal risk to participants. To ensure the safety of participant and integrity of the data, a data and safety monitoring plan (DSMP) is proposed as follows.

The PI will be primarily responsible for the study data and safety monitoring on a continuing basis. The PI is responsible for monitoring the progress of study, including recruitment, retention, study intervention adherence, completeness and quality of data collected, participant safety, and data confidentiality of study participants. The PI will be responsible for submitting annual study progress reports and adverse event reports to the program officer of NINR and University IRB. **The research team members** including the research coordinator, research assistants, and exercise intervention consults are responsible for reporting any adverse events immediately to the PI and informing the PI with any participant's safety concerns. The research team members are responsible for attending and participating in weekly or monthly team meetings. All research personnel will complete the Collaborative IRB Training Initiative (CITI) Basic Human Subjects Protection course and be certified prior to joining the research team.

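### Adverse events have no common method of elicitation, and contact during the 12 weeks is far more frequent in the intervention arm, so reported counts by arm may be biased towards more events there

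*Combined protocol and SAP*

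**What the plan says.** Section 8, Plan for Data and Safety Monitoring, sets a reporting duty: team members, including the exercise consultants, "are responsible for reporting any adverse events immediately to the PI". The paragraphs that follow describe what happens once an event has come to light: the PI reviews it with staff at once, and an independent clinician advises and meets the PI every three months. How an event comes to light is not stated.

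Contact during the treatment period is set out in section 4:

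- **Intervention arm, calls.** "Subjects will have biweekly phone consultation with the research team members to receive guidance and adjustment on activity plans". A research assistant also calls after three consecutive days of low activity (Self-monitoring).
- **Intervention arm, in person.** "All participants in the intervention group will have session 1 and session 2", with a third session if the trainer sees a need. There is also a 30-minute instruction session on the guideline and devices.
- **Control arm.** General education and a program book; otherwise participants "continue their daily activity and healthcare routine". No calls or visits are listed.

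Outside the 12 weeks the arms are treated alike: baseline collection, a phone call with instructions for the second Actigraph period, and a meeting after it. The measures listed for that meeting include no adverse event question. Section 7 (SAP) covers baseline comparisons, feasibility description and the Time × Group efficacy analysis; it contains no adverse event analysis.

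**The concern.** If events become known mainly when staff and participants talk, the arm with more conversations will tend to record more of them. Falls and injuries are the physical risk that section 8 names, and they also happen to people aged 60 to 85 who are in no exercise programme. A control arm could show that background rate, but only if its events are captured in a comparable way.

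Two features may widen the gap, though both are inferences. A fall or injury could itself cause three inactive days and so trigger a call, and controls have no equivalent. At the final meeting the open-ended interview is about the smartwatch and the intervention, which gives intervention participants more occasion to mention a problem.

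At stake is the descriptive safety record of a pilot whose first aim is feasibility and acceptability. Its event counts go into reports to the funder and the IRB and could inform a later trial.

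**Working it through.** **Step 1: contacts in the 12 weeks.** The documents give no adverse event rate or detection figure, so there is nothing to reproduce. The contact schedule can be counted from section 4.

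- Intervention: 12 weeks ÷ 2 = 6 calls, plus 2 or 3 sessions, so 6 + 2 = 8 to 6 + 3 = 9 scheduled contacts. Triggered calls and the instruction session are extra.
- Control: none listed beyond general education, whose timing is not given.
- Both arms afterwards: one instruction call and one meeting.

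A rule at the end of the Measurement text removes a participant who cannot be reached for a month or misses two appointments. It applies to both arms but sets no contact schedule.

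**Step 2: what unequal detection would do.** Inputs from the documents: "20 cognitively intact elders will be enrolled and randomly allocated to intervention or control group" (section 1), allocated 1:1 in blocks of 4 (section 4), so 20 ÷ 2 = 10 per arm. Assumptions, with no source in the documents: true risk r equal in both arms, detection 0.9 in the intervention arm, and 0.9, 0.6 or 0.3 in the control arm.

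Participants with a recorded event in an arm ~ Binomial(10, r × d), where d is detection. Expected count = 10 × r × d; for r = 10%, 10 × 0.10 × 0.9 = 0.90 against 10 × 0.10 × 0.6 = 0.60. The probabilities are exact sums over the two binomials.

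| True risk | Detection (int. vs control) | Expected counts | P(equal) | P(more in int.) |
|---|---|---|---|---|
| 5% | 0.9 vs 0.9 | 0.45 vs 0.45 | 0.49 | 0.25 |
| 5% | 0.9 vs 0.6 | 0.45 vs 0.30 | 0.54 | 0.29 |
| 5% | 0.9 vs 0.3 | 0.45 vs 0.15 | 0.58 | 0.33 |
| 10% | 0.9 vs 0.9 | 0.90 vs 0.90 | 0.33 | 0.33 |
| 10% | 0.9 vs 0.6 | 0.90 vs 0.60 | 0.36 | 0.41 |
| 10% | 0.9 vs 0.3 | 0.90 vs 0.30 | 0.38 | 0.50 |
| 20% | 0.9 vs 0.9 | 1.80 vs 1.80 | 0.23 | 0.38 |
| 20% | 0.9 vs 0.6 | 1.80 vs 1.20 | 0.24 | 0.52 |
| 20% | 0.9 vs 0.3 | 1.80 vs 0.60 | 0.21 | 0.68 |
| 30% | 0.9 vs 0.9 | 2.70 vs 2.70 | 0.20 | 0.40 |
| 30% | 0.9 vs 0.6 | 2.70 vs 1.80 | 0.19 | 0.59 |
| 30% | 0.9 vs 0.3 | 2.70 vs 0.90 | 0.14 | 0.78 |

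The ratio of expected counts is the ratio of detection probabilities whatever the risk: 0.9 ÷ 0.6 = 1.5, and 0.9 ÷ 0.3 = 3. In absolute terms the gap runs from 0.45 − 0.30 = 0.15 to 2.70 − 0.90 = 1.80 participants. The rows with equal detection show that chance alone often makes the arms differ at this sample size.

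**Step 3: recall at the final contacts.** Under Baseline data collection the 14-day Actigraph period follows randomisation. The treatment period is then 12 weeks, and the meeting follows 2 more weeks of Actigraph wear. Recall back to randomisation is at least 2 + 12 = 14 weeks at the instruction call and at least 2 + 12 + 2 = 16 weeks at the meeting.

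**The case against.** The strongest reply is that no planned analysis is touched. The SAP compares no event counts, and safety oversight works case by case: the PI reviews how serious each event was and what caused it, with independent clinical advice. A reader might infer that the PI and the monitor cannot judge causes without equal capture in controls. The documents do not support that, because individual review does not depend on the control rate. Only an arm-level comparison does.

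Second, discovery through contact is inferred. The quoted sentence is a reporting duty, not a detection method. Participants or their doctors may contact the team unprompted, and consent pages, which could hold instructions on reporting injuries, are not in the available text.

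Third, a reader might take the control arm to have no scheduled contact at all. That is true only of the 12 weeks. Both arms share baseline and post-intervention contacts, and the final meeting repeats earlier measures in both arms. A fall or injury with lasting consequences could surface there through pain, medication use, medical conditions or daily function.

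All three limit the point; none removes it. Those shared measures are not event questions, and no listed procedure asks either arm the same thing about adverse events.

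**Conclusion.** The point stands as a limited one. Followed as written, the plan would yield adverse event reports whose capture probably depends on arm, with an expected lean towards more in the intervention arm. This rests on the assumption that contact helps events come to light.

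A reader might go further and infer that counts will differ between arms. That is not supported. The bias is in the expected count, its size is unknown, and section 8 expects falls or injuries during activity only very rarely. At 5% risk and detection of 0.9 versus 0.6, both arms record zero with probability (1 − 0.045)^10 × (1 − 0.03)^10 = 0.63 × 0.74 = 0.47. Across the assumed risks of 5% to 30% at that detection, the arms tie with probability 0.54 down to 0.19, and the intervention arm shows more with probability 0.29 up to 0.59.

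The consequence is confined to how event counts by arm are described and read. The efficacy and feasibility analyses in the SAP are unaffected. This is a worthwhile improvement, not a serious flaw.

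**What to change.** Ask both arms the same short structured list (falls, injuries, urgent care, hospital stay since randomisation) at the post-intervention instruction call and again at the meeting, both of which already take place. Asking at the call shortens recall for events in the 12 weeks. Try to put the same list to participants who withdraw or are removed, when they leave. Otherwise a summary based on the final contacts would miss them, and some may have left because of an injury.

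Base any safety summary by arm on those answers. List events learned through coaching calls, trainer sessions and triggered calls separately, as intervention-arm information. Leave immediate reporting to the PI unchanged.

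The cost is a few added questions and no new visit. The drawback is long recall, at least 16 weeks at the meeting, so minor events will be under-reported; the same questions and timing should make that loss more similar between arms. Participants who cannot be reached after leaving remain a gap and should be counted by arm.
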